Appendix C Investigator Consent to the Use of Personal Information

Takeda will collect and retain personal information of Investigator, including his or her name, address, and other personally identifiable information. In addition, Investigator's personal information may be transferred to other parties located in countries throughout the world (eg, the United Kingdom, United States, and Japan), including the following:

- Takeda, its affiliates, and licensing partners.
- Business partners assisting Takeda, its affiliates, and licensing partners.
- Regulatory agencies and other health authorities.
- IRBs and IECs.

Investigator's personal information may be retained, processed, and transferred by Takeda and these other parties for research purposes including the following:

- Assessment of the suitability of Investigator for the study and/or other clinical studies.
- Management, monitoring, inspection, and audit of the study.
- Analysis, review, and verification of the study results.
- Safety reporting and pharmacovigilance relating to the study.
- Preparation and submission of regulatory filings, correspondence, and communications to regulatory agencies relating to the study.
- Preparation and submission of regulatory filings, correspondence, and communications to regulatory agencies relating to other medications used in other clinical studies that may contain the same chemical compound present in the study medication.
- Inspections and investigations by regulatory authorities relating to the study.
- Self-inspection and internal audit within Takeda, its affiliates, and licensing partners.
- Archiving and audit of study records.
- Posting Investigator site contact information, study details and results on publicly accessible clinical Study registries, databases, and websites.

Investigator's personal information may be transferred to other countries that do not have data protection laws that offer the same level of protection as data protection laws in Investigator's own country.

Investigator acknowledges and consents to the use of his or her personal information by Takeda and other parties for the purposes described above.

Appendix D Pregnancy and Contraception

Contraception and Pregnancy Avoidance Procedure

TAK-788 may pose a risk to developing fetuses or to babies who are being breastfed. Because TAK-788 may affect an unborn baby, female participants should not become pregnant while in this study, and male participants should not conceive with their female partner(s) while in this study. Women who are pregnant or breastfeeding will not be allowed to take part in this study.

Women of childbearing potential and male patients must use medically acceptable birth control. Avoiding sexual activity is the only certain way to prevent pregnancy.

Males Subjects and Their Female Partners:

It is not known whether the study medication will affect sperm or an unborn baby. Based on animal studies, taking TAK-788 may lead to testicular changes that could impact reproduction. For this reason, to be in the study males must agree not to father a child or donate sperm during the study and for 30 days after the last dose of TAK-788.

If a male has not had a vasectomy and is sexually active with any person who is pregnant, or could get pregnant, he must use a condom with spermicide each time he has sex during the study and for 30 days after last dose of TAK-788. No restrictions are required for a vasectomized male provided his vasectomy has been performed 4 months or more prior to the first dosing of study drug. A male who has been vasectomized less than 4 months prior to study first dosing must follow the same restrictions as a non vasectomized male and must agree to use an appropriate method of barrier contraception (latex condom with a spermicidal agent) during the entire study, and for 30 days after his last dose of TAK-788. Or, he should completely avoid having heterosexual intercourse.

If a female partner does become pregnant while a male subject is taking part in the study, the subject must tell the study doctor immediately.

In this situation, the female partner should be under medical supervision during her pregnancy, and the baby should be under supervision after it is born. The female partner may be asked to give her consent to the collection of information related to both herself as well as the baby.

Acceptable birth control for males with female partners includes any of the following:

- total abstinence (no sexual intercourse) if it agrees with his preferred and usual lifestyle
- a barrier method (latex condom with a spermicidal agent)

Males must use acceptable birth control during the study treatment period and for at least 30 days after their last dose of TAK-788 and should tell their female partner(s) that they are in research study.

Females:

Females must agree not to become pregnant, breastfeed a baby or donate an egg or eggs (ova) during the study and for 30 days after the last dose of TAK-788. Women of childbearing potential must use acceptable birth control from the time of signing the informed consent form until at least 30 days after their last dose of TAK-788.

If a female has been surgically sterilized or is postmenopausal, she does not need to meet any contraception requirements to take part in this study. If a female is of childbearing potential and is sexually active with a male partner, she must be willing to use an acceptable method of contraception during the study and for 30 days after the last dose of TAK-788.

TAK-788 may decrease effectiveness of hormonal contraceptives, therefore, women of childbearing potential must use effective non-hormonal methods of contraception. Acceptable birth control for women of childbearing potential with male partners must include one form of highly effective non-hormonal contraception and one additional effective (barrier) method, as described below:

Highly effective non-hormonal methods	Additional effective (barrier) methods
Non-hormonal intrauterine device	Male or female condom with or without spermicide (female and male condoms should not be used together)
Vasectomised sole sexual partner (removal of the tube that carries sperm from the testicle to the penis)	
Sexual abstinence (no sexual intercourse, additional effective barrier method therefore not applicable)	Cap, diaphragm or sponge with spermicide

Total abstinence (no sexual intercourse) may be considered an acceptable method of birth control if it agrees with her preferred and usual lifestyle.

In order to enter the study, all females must have a pregnancy test to confirm that she is not pregnant. This test will be repeated just before she starts taking the first study medication and then regularly throughout the study, at each check-in. If a pregnancy test during the study shows that she may be pregnant, she will be withdrawn from the study and the treatment will end. She will be asked for the results of any tests and procedures carried out during pregnancy and up to the birth. She may also be asked for the results from any evaluation of the baby after the birth.

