3.0 SCHEDULE OF STUDY PROCEDURES

Study Procedures ^a	S ^b	Study Days in Periods 1 and 2 ^c														EOS or ET ^p	FU ^q	
		Days in Period →		1										2	3	4	6	
		Hours →	C-I ^d	0	0.5	1	2	4	6	8	12	24	48	72	120	168	240	
Administrative Procedures																		
Informed Consent	X																	
Inclusion/Exclusion Criteria	X	X ^f																
Medical History	X																	
Safety Evaluations																		
Full Physical Examination ^g	X																	
Height	X																	
Weight	X	X ^h																
12-Lead Safety ECG	X		X ^k					X									X	
Vital Signs (HR and BP)	X		X ^k					X			X	X					X	
Vital Signs (RR and T)	X																X	
Pulmonary function test ^l	X																	
Hem, Serum Chem ^j , and UA	X	X ^l										X					X	
Serum Pregnancy Test (♀ only)	X	X																
Serum FSH (PMP ♀ only)	X																	
Urine Drug and Alcohol Screen	X	X																
HIV/Hepatitis Screen	X																	
AE Monitoring	X											X						
ConMeds Monitoring												X						

CONFIDENTIAL

Study Procedures ^a	S ^b	Study Days in Periods 1 and 2 ^c													EOS or ET ^p	FU ^q	
		-1		1							2	3	4	6	8	11 ^e	
		Hours →	C-I ^d	0	0.5	1	2	4	6	8	12	24	48	72	120	168	240
Study Drug Administration / PK																	
TAK-788 Administration				X													
Blood for TAK-788 and metabolites (AP32960 and AP32914) PK				X ^m	X	X	X	X	X	X	X	X	X	X	X	X ⁿ	
Other Procedures																	
Confinement in the CRU ^o										X							
Visit and Return Visits	X																

- a. For details on Procedures, refer to Section 9.0.
- b. Within 21 days prior to the first study drug administration.
- c. There will be a washout period of 10 days between the dose in Period 1 and the dose in Period 2.
- d. Subjects will be admitted to the CRU on Day -1 of Period 1, at the time indicated by the CRU.
- e. Day 11 of Period 1 will be the same as Day 1 of Period 2. Study procedures will only be performed once.
- f. To be conducted in Period 1 only.
- g. Symptom-driven physical examinations may be performed at other times, at the PI's or designee's discretion.
- h. If the screening assessment was conducted within 4-7 days prior to the first dosing (Day 1 of Period 1), assessment will be conducted at check-in only if, in the opinion of the Investigator, there is reason to believe they have substantially changed.

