- i. Pulmonary function tests may be performed in the event of a pulmonary AE and deemed clinically necessary, as determined by the Investigator or designee.
- j. Samples for serum chemistry will be obtained following a fast of at least 8 hours, however, in case of dropouts or rechecks, subjects may not have fasted for 8 hours prior to the serum chemistry sample being taken.
- k. To be performed within 24 hours prior to dosing.
- l. To be repeated prior to dosing in Period 2.
- m. Prior to dosing.
- n. The Period 1 Day 11 PK sample will serve as the pre-dose PK sample for Period 2.
- o. Subjects will start confinement on Day -1 of Period 1 and will be released from confinement after the 240-hour study assessments in Period 2 are completed. At all times, subjects may be required to remain at the CRU for longer at the discretion of the Investigator or designee.
- p. To be performed at the end of Period 2 or prior to early termination from the study.

Study Procedures ^a		S ^b	Study Days in Periods 1 and 2 ^c														
Days in Period →			-1	1							2	3	4	6	8	11 ^e	
Hours →	C-I ^d		0	0.5	1	2	4	6	8	12	24	48	72	120	168	240	EOS or ET ^p

q. The clinic will contact all subjects (including subjects who terminate the study early) 30 ± 2 days after the last TAK-788 dose to determine if any AEs have occurred since the last study visit.

Abbreviations: ♀ = Females, AE = Adverse events, BP = Blood pressure, C-I = Check-in, Chem = Chemistry, ConMeds = Concomitant medication, CRU = Clinical research unit, ECG = Electrocardiogram, EOS/ET = End-of-Study or early termination, FSH = Follicle-stimulating hormone, FU = Follow-up, Hem = Hematology, HIV = Human immunodeficiency virus, HR = Heart rate, PI = Principal Investigator, PK = Pharmacokinetics, PMP = Postmenopausal, Preg = Pregnancy, RR = Respiratory rate, S = Screening, T = Temperature, UA = Urinalysis

Table 3.a Pharmacokinetic Plasma Concentration Sampling Schedule

Study Day	Sample Collection Time	Time (Relative to Dosing) h:min	Plasma Concentrations of TAK-788, AP32960, and AP32914
1 (Period 1)	0 h (predose)	00:00 ^a (predose)	✓
	0.5 h	00:30 (±5 min)	✓
	1 h	01:00 (±10 min)	✓
	2 h	02:00 (±10 min)	✓
	4 h	04:00 (±10 min)	✓
	6 h	06:00 (±20 min)	✓
	8 h	08:00 (±20 min)	✓
	12 h	12:00 (±20 min)	✓
	2	24:00 (±30 min)	✓
	3	48:00 (±30 min)	✓
4	0 h	72:00 (±60 min)	✓
6	0 h	120:00 (±60 min)	✓
8	0 h	168:00 (±60 min)	✓
11 (Predose Day 1 Period 2)	0 h	240:00 (±60 min) ^{a,b} (predose)	✓
	0.5 h	00:30 (±5 min)	✓

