7.5 Criteria for Discontinuation or Withdrawal of a Subject

Subjects are free to withdraw from the study at any time for any reason.

In addition, subjects may be withdrawn from the study by the Investigator or designee for the following reasons:

- AEs.
- A positive pregnancy test for females.
- Positive urine drug or alcohol results.
- Difficulties in blood collection.
- Taking prohibited concomitant medications.
- Emesis within 8 hours post dose.

A subject may be withdrawn by the Investigator (or designee) or the Sponsor if enrollment into the study is inappropriate, the study plan is violated, or for administrative and/or other safety reasons

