 - c) that personal information (including personal health information) may be added to Takeda's research databases for purposes of developing a better understanding of the safety and effectiveness of the study medication(s), studying other therapies for patients, developing a better understanding of disease, and improving the efficiency of future clinical studies;
 - d) that subjects agree not to restrict the use and disclosure of their personal information (including personal health information) upon withdrawal from the study to the extent that the restricted use or disclosure of such information may impact the scientific integrity of the research; and
 - e) that the subject's identity will remain confidential in the event that study results are published.

25. Female subjects of childbearing potential (eg, nonsterilized, premenopausal female subjects) who are sexually active must use highly effective contraception (as defined in the informed consent) from signing the informed consent and throughout the duration of the study, and for 30 days after the last dose of study drug. Regular pregnancy tests will be performed throughout the study for all female subjects of childbearing and non-childbearing potential. If a subject is found to be pregnant during study, study drug will be discontinued and the Investigator will offer the subject the choice to receive unblinded treatment information.
26. Male subjects must use highly effective contraception (as defined in the informed consent) from signing the informed consent throughout the duration of the study and for 30 days after the last dose of study drug. If the partner or wife of the subject is found to be pregnant during the study, the Investigator will offer the subject the choice to receive unblinded treatment information.
27. A statement that clinical Study information from this Study will be publicly disclosed in a publicly accessible website, such as ClinicalTrials.gov.

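### The protocol contradicts itself on the number of check-ins and pregnancy tests, so it is unclear whether any test is scheduled before the second dose

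*Protocol*

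**What the plan says.** **Testing as promised.** Protocol Appendix D (Females) requires a test for entry, a repeat before the first study medication, and further tests after that: "then regularly throughout the study, at each check-in". Appendix B item 25, one of the elements of informed consent, states: "Regular pregnancy tests will be performed throughout the study for all female subjects of childbearing and non-childbearing potential".

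**Testing as scheduled.** In Section 3.0 the serum pregnancy row carries two marks, at screening and at check-in (C-I, Day -1). It has no mark on later study days or at end of study/early termination (EOS/ET), and neither mark carries a footnote.

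**Number of check-ins.** Footnote d, attached to C-I, reads "Subjects will be admitted to the CRU on Day -1 of Period 1, at the time indicated by the CRU". Footnote o and notes b and d of the Section 2.0 schematic describe confinement from that day until the 240-hour assessments of Period 2. However, the Day -1 column sits under the heading "Study Days in Periods 1 and 2". Protocol Sections 1.0 and 6.1 and SAP Section 4.4 describe admission on the day before dosing in each period, and Section 9.3.4 describes Day -1 housing in each period. SAP Section 7.12.2 places safety laboratory tests at a check-in on Day -1 of each period.

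**Consequence of a positive test.** Section 7.5 lists "A positive pregnancy test for females" among reasons for which the investigator may withdraw a subject. Appendix D makes withdrawal and the end of treatment automatic.

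**The concern.** Women of childbearing potential may enrol, and Appendix D says the drug may pose a risk to a developing fetus. Each subject receives two 160 mg doses 10 days apart. Appendix D ties testing during the study to check-ins, so the number of check-ins determines whether a test is scheduled before the second dose.

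A site working from footnotes d and l would have no scheduled pregnancy test before that dose. A site working from Section 6.1 would have one. A conception shortly before Day -1 of Period 1, too recent to show then, is the case in which this difference matters. The consent elements also describe regular testing that the schedule does not show.

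**Working it through.** No statistical figure bears on this point. The check is a comparison of passages, a count of scheduled tests and simple day arithmetic.

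**Inputs**
- Day -1 is the day before Day 1 (SAP Section 7.1.1.1): 1 day.
- First dose to second dose (Section 3.0, footnote c): 10 days.
- Second dose to release (footnote o): 240 hours = 10 days.
- Second dose to follow-up call (footnote q): 30 ± 2 days.

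**Count under each reading**

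| | One check-in | Check-in in each period |
|---|---|---|
| Scheduled tests | 2 (screening; Day -1 of Period 1) | 3 (screening; Day -1 of Periods 1 and 2) |
| Last scheduled test to second dose | 1 + 10 = 11 days | 1 day |
| Scheduled tests after second dose or at EOS/ET | 0 | 0 |

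On the one-check-in reading, subjects are released about 1 + 10 + 10 = 21 days after the last scheduled test. The follow-up call comes about 1 + 10 + 30 = 41 (± 2) days after it.

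**The footnotes do not settle which reading is meant**
- Footnote l, "To be repeated prior to dosing in Period 2", is attached to the check-in mark for hematology, chemistry and urinalysis. It would be unnecessary if every check-in item recurred in Period 2. The pregnancy row lacks it, which suggests no repeat.
- Footnote f limits an item to Period 1 and is attached to the check-in mark for eligibility criteria. It would be unnecessary if every check-in item applied to Period 1 only. The pregnancy row lacks it too, which suggests a repeat.
- Footnote e makes Day 11 of Period 1 the same day as Day 1 of Period 2. Day -1 of Period 2 is therefore Day 10 of Period 1, which has no separate column.
- The eligibility criteria (Section 7.1 item 4, Section 7.2 item 8) refer to a first check-in, which implies more than one.

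**What goes unmet**
If there is one check-in, testing at each check-in is literally satisfied. If there are two, the schedule can be read as satisfying it. Regular testing throughout the study is hard to find on either reading, because nothing is scheduled after the second dose.

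**Withdrawal wording**
Section 7.5 is permissive. Appendix D is mandatory, and Appendix B item 25 also says study drug will be discontinued if a subject is found to be pregnant.

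**The case against.** The strongest reply is that the schedule already provides a test before the second dose. The column heading covers both periods, several sections in both documents place Day -1 in each period, and the row is not restricted to Period 1. This is a fair reading and may be the intended one. It does not remove footnotes d and o or the missing footnote l, so what stands is that the documents disagree.

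A reader might infer that there is definitely only one check-in, and that the withdrawal rule therefore cannot operate after Day -1 of Period 1. The documents do not support either step. The first rests on one of two competing readings. The second fails even on that reading: Section 7.5 acts on any positive test, scheduled or not, and Section 9.2.9 allows unscheduled laboratory tests at the investigator's discretion. The most that can be said is that, with one check-in, no *scheduled* test could trigger the rule after that day.

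Three further objections have some force:
- **Appendix B looks like template text.** It offers unblinded treatment information in an open-label study and mentions PGx results although Section 9.3.3 says PGx is not applicable. It is weak evidence of study-specific intent, but Appendix D, which names TAK-788 throughout, makes a similar promise.
- **Other safeguards exist.** These are two tests before the first dose, exclusion for a positive test, a highly effective non-hormonal contraceptive method plus a barrier method (or abstinence) from consent, and confinement on the one-check-in reading. They reduce the risk but do not detect a conception shortly before Day -1.
- **The schedule was read from a table with a broken header.** The count of two marks in the pregnancy row is clear. Their placement at screening and check-in is consistent with the urine drug row, which has the same pattern and which Section 7.2 item 8 ties to screening and first check-in.

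**Conclusion.** The inconsistency is real and should be corrected. It concerns subject protection and the accuracy of the consent elements; it does not touch the PK endpoints, the sample size or the analysis.

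The last scheduled pregnancy test falls either 11 days or 1 day before the second dose, depending on which passages a site follows. No test is scheduled after the second dose or at EOS/ET on either reading, although the appendices promise regular testing throughout. Whether a positive test leads to optional or mandatory withdrawal also differs between sections.

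This rests on the two marks in the pregnancy row being at screening and check-in. The size of the residual risk cannot be given: the documents state neither the number of women among the 14 planned subjects nor how soon after conception the test turns positive. The consent form was not available, so what subjects are actually told could not be checked.

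**What to change.** Reconcile Section 3.0 and its footnotes, Sections 6.1, 7.5 and 9.3.4, Appendix B item 25 and Appendix D so that three things agree throughout: the number of check-ins, the pregnancy-test time points, and the withdrawal wording. Align Section 1.0 and SAP Sections 4.4 and 7.12.2 with the chosen description of check-in. The sponsor and investigator must decide which time points and which wording apply; this review does not propose one.

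The cost is protocol and consent wording. If the decision adds tests, it is one or two assays per female subject, at most 2 × 14 = 28 if all planned subjects were women and before any replacements. The schedule already has safety blood drawn before Period 2 dosing and at end of study, and the pregnancy test is a serum test, so no extra visit would be needed. If the decision is to keep the two marks as they stand, the appendices need rewording and no assays are added.

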### **3.0 LIST OF ABBREVIATIONS**

AE	adverse event
ANOVA	analysis of variance
AUC	area under the curve
AUC extrap%	percent of AUC ∞ extrapolated
AUC ∞	area under the concentration-time curve from time 0 to infinity
AUC last	area under the concentration-time curve from time 0 to the time of the last quantifiable concentration
BLQ	below the limit of quantitation
BMI	body mass index
CI	confidence interval
CL/F	apparent clearance after extravascular administration
C max	maximum observed concentration
CPAP	clinical pharmacology analysis plan
CRF	case report form
CS	clinically significant
DMP	Data Management Plan
ECG	electrocardiogram
FDA	Food and Drug Administration
FE	food effect
GMR	geometric mean ratio
ICF	informed consent form
IND	Investigational New Drug
λ z	terminal disposition phase rate constant
LSM	least-squares mean
MedDRA	Medical Dictionary for Regulatory Activities
MPR	metabolite to parent ratio
NDA	New Drug Application
PFT	pulmonary function test
PI	Principal Investigator
PK	pharmacokinetics
SAE	serious adverse event
SAP	statistical analysis plan
SD	standard deviation
SOC	System Organ Class
t ½z	terminal disposition phase half-life
TEAE	treatment-emergent adverse event
TFL	tables, figures, and listings
t max	time of first occurrence of C max
V z/F	apparent volume of distribution during the terminal disposition phase after

WHO extravascular administration  
World Health Organization

